## **PHILUCA: The Development of Muscle Mass, Muscle Strength, and Muscle Function in Patients With Lung Cancer During Cancer Treatment**

### **Updated power considerations and sample size**

The sample size calculation was originally based on a pooled estimate from prospective cohorts of patients with advanced-stage lung cancer, assuming a hazard ratio for mortality of 2.38 and a sarcopenia prevalence of 50%. With power set at 90% and a two-sided alpha of 0.05, a final sample of 130 patients with advanced-stage lung cancer was required for the primary analysis.

Initially, an expected study withdrawal rate of **28%** was assumed, corresponding to a required baseline inclusion of **180 patients** with advanced-stage lung cancer to ensure 130 patients available at 3-months follow-up.

However, based on observed study retention during recruitment, the actual withdrawal rate has been lower than anticipated. As of **05 February 2026**, among the first **153 included patients**, the observed dropout rate was **19%**. Under this empirically observed retention rate, inclusion of **160 patients** with advanced-stage lung cancer is sufficient to ensure the required final sample size of 130 patients.

Accordingly, the target sample size for patients with advanced-stage lung cancer has been revised from 180 to **160 patients**, without compromising the statistical power of the study.

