### Studyprotocol, v.1.3 20.12.2024

have to include 130 patients with advanced stage lung cancer. To account for an expected study withdrawal rate of approximately 28%, we need to ensure that we have 130 patients remaining by the end of the study. To find the initial number of participants required, we divide the final required sample size (n=130) by the retention rate (0.72). Rounded up to the nearest whole number, we need to include 180 patients with advanced stage lung cancer. Our recruitment method (at time of referral for suspicion of lung cancer) will include non-cancer patients, patients at low stage who undergo surgery, which means the total cohort will include n=500 participants, to ensure 180 patients with advanced stage lung cancer. This total cohort will enable subgroup analyses comparing cancer and non-cancer participants, as well as analyses within different treatment subgroups.

We will stratify analyses according to relevant categories in uni- and multivariate regression analyses examine associations between exposures and outcomes, presenting estimates of regression coefficients and odds ratios with 95% confidence intervals and p-values and use mixed effect models for repeated measurements.

For the social vulnerability screening instrument, we will describe the distribution of each factor included in the vulnerability screening tool. Next, we will use statistical analysis ('prediction models') to select the vulnerability factor that best predicts treatment adherence (measured in Relative Dose Intensity). Furthermore, we will examine the sensitivity and specificity of the screening tool using different cut-off scores to assess the optimal cut-off for identifying patients who did not completed treatment optimally.

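### The revised target of 160 falls just short of 130 at the stated 19% dropout (the protocol's own rule gives 161), and the 19% is used as a fixed rate without its uncertainty or its population

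*Protocol*

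**What the plan says.** The section on updated power considerations and sample size, at the front of the protocol, restates the basis of the calculation: "assuming a hazard ratio for mortality of 2.38 and a sarcopenia prevalence of 50" per cent. It continues "With power set at 90% and a two-sided alpha of 0.05", and concludes that "a final sample of 130 patients with advanced-stage lung cancer was required for the primary analysis".

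For losses, "an expected study withdrawal rate of 28% was assumed" at first, which led to 180 inclusions so that 130 would be available at the 3-month follow-up. The update then reports that, as of 05 February 2026, in the first 153 patients included, "the observed dropout rate was" 19%. From this it concludes that 160 patients "with advanced-stage lung cancer is sufficient to ensure the required final sample size of 130 patients". It lowers the target from 180 to 160, "without compromising the statistical power of the study".

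The method is given in section 6.1: divide 130 by the retention rate, 0.72 at that time, and round up. The result is worded "Rounded up to the nearest whole number, we need to include 180 patients with advanced stage lung cancer".

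Three other places bear on the point. Section 6.1 says that recruitment at referral also brings in non-cancer and low-stage surgical patients. Sections 5.4.1 and 7.1 say that participants without lung cancer have no assessments after baseline. Table 1 in section 5.5.1 and section 7.1 say that survival, the primary outcome, is taken from medical records.

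**The concern.** Two things are wrong or unsupported in the reduction to 160.

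- **Arithmetic.** The stated rate and the stated rounding rule do not give 160. The update says that 130 is assured, when its own inputs put the expected number slightly below 130.
- **The rate.** The 19% is an estimate taken during recruitment, used as if it were known. The target is defined by availability at 3 months in advanced-stage patients. The sentence that reports the rate states neither the stage of the 153 nor whether their 3-month visit had fallen due.

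At stake is the current justification for the size of the primary analysis. The design itself is not in danger. What needs correcting is a statement of certainty that the figures do not carry.

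**Working it through.** **Inputs from the protocol.** Required final number 130, hazard ratio 2.38, sarcopenia prevalence 50%, power 90%, two-sided alpha 0.05, observed dropout 19% in 153 patients, revised target 160 (sample size update); division by the retention rate with rounding up (section 6.1).

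**1. The inclusion target.** Formula: N = 130 / (1 − dropout), rounded up.

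- Revised: 130 / 0.81 = 160.49, so 161. The protocol states 160.
- Expected retained: 160 × 0.81 = 129.6; 161 × 0.81 = 130.4.
- The superseded target has the same slip: 130 / 0.72 = 180.56, which rounds up to 181, not 180. This has no remaining consequence.

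The stated 160 is thus reproduced to within one patient, but the rounding went down, not up.

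**2. Chance of reaching 130 if the true dropout is exactly 19%.** Binomial probability of at least 130 retained:

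| Included | Probability |
|---|---|
| 160 | 51.6% |
| 161 | 58.0% |
| 168 | 90.0% |

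**3. Uncertainty of the 19%.** The number of dropouts is not given. Of 153 patients, only 29 rounds to 19%: 28/153 = 18.3%, 29/153 = 18.95%, 30/153 = 19.6%. The exact (Clopper-Pearson) 95% interval for 29/153 is 13.1% to 26.1%. Applied to 160 inclusions:

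- at 13.1% dropout, about 139 retained;
- at 26.1% dropout, about 118 retained.

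**4. Effect on power.** Deaths needed by the Schoenfeld formula: (1.960 + 1.282)² / (0.25 × (ln 2.38)²) = 10.51 / (0.25 × 0.7519) = 55.9, so 56. The protocol states no event count or event proportion. The table assumes that 130 patients yield 56 deaths (56/130 = 43%) and scales deaths with the number retained. Power = Φ(√(deaths × 0.25) × 0.8671 − 1.960).

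| Retained | Deaths (assumed 43%) | Power |
|---|---|---|
| 130 | 56.0 | 90.05% |
| 129.6 | 55.8 | 89.96% |
| 118 | 50.8 | 87.1% |
| 139 | 59.9 | 91.8% |

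The rounding slip costs about 0.1 percentage point. The whole interval for the dropout rate moves power between about 87% and 92%.

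**The case against.** **The slip is trivial.** It is one patient, or 0.4 of a patient on average, and power stays at 90% to the nearest point. This stands. It limits the size of the point but does not make the claim of assurance correct.

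**The roughly even chance of reaching 130 is not a defect of 160.** Dividing by retention aims at the expected number, so it always gives about an even chance; 161 reaches only 58%. The protocol sets no assurance criterion, so 168 inclusions for a 90% chance would be a preference, not a correction. This stands too. The probability shows only that *ensure* is the wrong word.

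**The 153 may be the right group.** The sentences around the rate concern advanced-stage patients, and the word *first* may mark a leading subset whose follow-up is complete. That reading is possible, but the text does not say so.

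A reader might infer the opposite: that patients included after about 5 November 2025 are in the denominator and could not yet have missed a 3-month visit, so that 19% is too low. If 153 were the whole accrual and had arrived evenly since 01.09.2024, about 27 would have had less than 3 months, and dropout in the rest would be about 21% to 23%. The documents do not support this inference. They do not say that 153 is the whole accrual or that it was even, and the 23% also needs all 29 dropouts to fall among the other 126. What remains is an omission: stage and follow-up status are not stated.

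**Missing the 3-month visit need not remove a patient from the primary analysis.** Survival comes from medical records, so a patient with baseline measurements and continuing consent for record access can still contribute. This is a sound defence of 160, but the update does not use it. It defines the requirement as patients available at 3 months.

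**Conclusion.** The point holds, and it is minor. By the protocol's own method the target is 161; 160 gives 129.6 expected, so the statement that 130 is assured is wrong as written. The 19% is an unqualified estimate taken during recruitment. Its sampling error alone spans about 118 to 139 retained of 160, and the update does not tie it to advanced-stage patients past 3 months.

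A reader might go further and infer that power is compromised. The documents do not support that: the rounding alone costs about 0.1 percentage point, and even 118 retained leaves about 87%. The accurate criticism is that the claim of uncompromised power is asserted without a range.

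These conclusions rest on 29 dropouts (the only count that rounds to 19% of 153) and, for power, on 56 deaths among 130 patients, which is an assumption because the protocol gives no event count.

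**What to change.** 1. Recompute dropout only in advanced-stage patients whose 3-month date had passed by 05 February 2026, and report the numerator, the denominator and the interval.
2. With that rate, restate the target. If 19% stands, write 161, or keep 160 and say that it is expected to yield about 130, with the range.
3. Replace the claims that 130 is ensured and that power is uncompromised with the retained number and the power that follow from it.

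Alternatively, keep 160 and change the basis. State that survival is taken from medical records, so that patients who miss the 3-month visit but keep consent for record access still count in the survival analysis. Then give the target in deaths: about 56 for a hazard ratio of 2.38, 50% prevalence, 90% power and two-sided alpha 0.05.

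Either route costs one recalculation from data in hand and a few changed sentences. No extra patients are needed.

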### **Update to data collection timepoints**

The study protocol was amended with respect to the timing of follow-up assessments.

Due to logistical and time constraints in the clinical setting, it was not possible to assess changes in muscle parameters or health-related quality of life beyond **three months after inclusion**. Furthermore, repeated assessments of muscle parameters at each chemotherapy cycle during first-line treatment could not be performed, as these timepoints coincided with treatment administration and clinical workflows that did not allow for additional study procedures.

As a result, follow-up assessments were limited to a single post-baseline timepoint. Assessments are intended to be performed approximately **three months after inclusion**, which in routine clinical practice usually corresponds to the timepoint immediately **prior to the first control imaging scan**. This timing ensures clinical relevance while maintaining feasibility and minimizing participant burden.

These changes do not affect the primary study objectives but define the scope of longitudinal analyses accordingly.

**Declaration from investigators and collaborators**

The investigators and collaborators of this trial declare no conflicts of interest and that the trial will be conducted in accordance with the Declaration of Helsinki, and the respective rules and regulations in Denmark.

**Authorships**

This protocol was authored by abovementioned study group. First- and co-authorships of the scientific publications with experiences and findings from the project will follow the Vancouver guidelines.

## 2.0 Introduction

Low socioeconomic position (SEP) is strongly associated with lung cancer incidence and survival. Barriers related to receiving recommended treatment among lung cancer patients with low SEP may include adverse health behavior, long distances to the hospital, and limited physical and psychosocial resources. Other biological barriers related to treatment receipt include the development of sarcopenia, which is the natural degeneration of the body with a gradual reduction in muscle mass and physical performance. A cancer disease and treatment can further accelerate sarcopenia substantially, thus enhancing the risk of cancer cachexia, which involves sarcopenia along with weight loss. Sarcopenia and cachexia are highly prevalent among patients with lung cancer, and emerging evidence suggests an association between these factors and worse treatment outcomes. Progressive cancer-related sarcopenia and cachexia is multifactorial and self-enhancing and with current knowledge incompletely explaining underlying mechanisms, an efficient management strategy is lacking. Exploring these factors as well as patient-related barriers to treatment may provide an

## Appendiks 2

### Studyprotocol, v.1.3 20.12.2024

opportunity to improve lung cancer treatment receipt and tolerance and thus prognosis by informing the treatment plan and intervening timely and appropriately to prevent or improve sarcopenia and cachexia.

## 3.0 Background

Lung cancer has one of the worst prognoses among cancers, especially for patients with low SEP and advanced disease . Differences in received treatment, stage, and comorbidity may explain a large proportion of the social inequality in lung cancer prognosis both among early-stage and advanced-stage patients . Thus, both disease-related factors as well as social and behavioral factors may increase the risk of not adhering to lung cancer treatment. Patients with lung cancer often have poor Eastern Cooperative Oncology Group performance status (PS)  at the time of diagnosis resulting in a high burden of side effects, treatment delays, dose-reductions and treatment failure . Chemotherapy is primarily offered to patients with a PS of 0-2. Yet, this measure is not an ideal parameter, and in particularly in older patients with cancer, determination of PS is often inaccurate . The dose of chemotherapy is routinely calculated based on patient's body surface area. This method might be problematic i.e. in patients with sarcopenic obesity, as the combination of a large body surface area and low muscle mass may lead to a lower tolerance for chemotherapy and a worse prognosis . Further, initial dose downregulation is based on the patient's age, comorbidity and/or PS. Taken together, it appears that the tools available for physicians to precisely judge if downregulation is appropriate may be insufficient. Even patients with a good PS at time of diagnosis are at risk of developing sarcopenia or cachexia through the course of systemic treatment . This receives little focus in the clinic, although it could provide a potential patient benefit in terms of intervening prior to a loss in physical function and reduced Quality of Life (QoL) . If an intervention could be successful in preventing or reversing sarcopenia or cachexia, it can potentially increase patients' chance of completing the scheduled treatment regime. Emerging evidence suggests that resistance training and protein rich diet may have this effect , but studies in patients with lung cancer during systemic treatment are lacking .

There is marked diversity in current clinical practice in assessing the degree of muscle loss in patients with cancer and in quantifying its functional implications . If the loss of muscle mass and strength have significant clinical implications for patients with cancer, then standardized, validated diagnostic

## Appendiks 2

### Studyprotocol, v.1.3 20.12.2024

thresholds are clearly needed. Furthermore, while the effects of sarcopenia have been extensively studied in the elderly patients, factors associated with loss of muscle mass and strength in cancer remain unclear.

The prevalence of sarcopenia in lung cancer is higher than in other cancers, ranging from 22-71% depending on the population and definition of sarcopenia, however, no studies have described the prevalence in a Danish lung cancer population. Among associated clinical factors identified in previous studies are older age, smoking, comorbidity, low BMI, low caloric intake, physical inactivity, cancer treatment and progression. The knowledge about underlying mechanisms of sarcopenia in cancer is, however, fragmented, and it remains to be uncovered what happens in real life patients and if it can be influenced by an intervention. Further, with the relatively poor prognosis in lung cancer, it is important not only to explore if survival time may be improved, but also if QoL during treatment and survival time can be improved.

Taken together, with the lack of knowledge about patient-related factors and sarcopenia and cachexia prevalence and development, there is a need to explore what influences the individual patient's treatment tolerance, QoL and prognosis. Further, this may provide an opportunity to explore if clinical tools covering social vulnerability, as well as muscle mass and physical function tests, can add valuable and precise information that may be used to better judge the optimal systemic treatment dose and to better identify patients in need of support and symptom management during treatment. Finally, due to the high risk of losing physical function and developing sarcopenia and cachexia in patients with lung cancer, there is a serious need for developing effective interventions that can prevent or restore physical function and muscle mass throughout treatment and into survivorship.

## 4.0 Aims

The overall aims of the PHILUCA study are in a longitudinal study to examine sarcopenia and cachexia risk factors, the development over time, and the associations with lung cancer treatment tolerance, QoL and prognosis. In addition, the aim is to test whether a vulnerability screening tool can identify patients at high risk of not completing the planned treatment.

## Appendiks 2

### Studyprotocol, v.1.3 20.12.2024

#### 4.1 Research Question and hypothesis

What is the prevalence and pattern of development of sarcopenia and cachexia and what are the associated factors, prognosis, treatment tolerance and QoL throughout treatment?

We hypothesize that if the Danish stage distribution of sarcopenia and cachexia is worse than that of other countries - and health is worse than that of other countries, then the risk of sarcopenia and cachexia might also be higher and could explain why we have a relatively larger subgroup of patients with lung cancer who have low 1-year survival rates.

Which patient-related and disease-related factors from can best predict treatment adherence as part of a vulnerability screening instrument?

We hypothesize that selected patient-related and disease-related factors can contribute to a vulnerability scale and that this scale is able to predict treatment adherence.

## 5.0 Methods

### 5.1 Patient and public involvement

The design of PHILUCA has been developed and refined by the patient panel of Zealand University Hospital, consisting of former or current cancer patients and their relatives. The patient panel has by the 13th of May 2024 recognized the project's relevance and approved the quantity and type of data collection methods.

### 5.2 Study design and setting

The PHILUCA study will be a prospective cohort involving 180 participants and will be conducted at the Department of Oncology and Palliative Care at Zealand University Hospital (ZUH) in Næstved. This allows us to investigate the prevalence, patterns of development, and impact of sarcopenia and cachexia throughout the patient's treatment as well as patient and disease-related factors associated with treatment adherence. This approach allows for the identification of associated factors and provides real-time data, ensuring accuracy and reliability.

## Appendiks 2

### Studyprotocol, v.1.3 20.12.2024

## 5.3 Population

### 5.3.1 Inclusion criteria

- Patients newly diagnosed with histologically verified lung cancer and scheduled for oncological treatment
- Age > 18 years
- Expected survival > 3 months

### 5.3.2 Exclusion criteria

- Competing cancer
- Pregnancy
- Physical or cognitive disabilities preventing participation
- Not able to understand written and verbal Danish

## 5.4 Study Procedure

### 5.4.1 Recruitment procedure

Patients with suspected lung cancer will be recruited from the Department of Pulmonary Medicine, Zealand University Hospital (ZUH), Næstved. According to reports from the Department of Pulmonary Medicine, > 70% of cases patients will be diagnosed with lung cancer, but in the approximately 30% of patients where a lung cancer diagnosis is not confirmed we omit follow-up assessments. This will thoroughly be explained to the patient verbally and in the written information leaflet during invitation.

Moreover, eligible candidates not already identified from Department of Pulmonary Medicine, will be identified during the multidisciplinary team (MDT) lung cancer conference within the Department of Clinical Oncology and Palliative Care. Subsequently, following a comprehensive medical examination during their initial outpatient visit, patients meeting the specified inclusion criteria will be approached by the attending physician regarding potential participation in the study.

It is important to emphasize that patient recruitment may occur at two distinct time points: first, during the diagnostic phase when suspicion of lung cancer arises, and second, during the initial outpatient visit at the Department of Clinical Oncology and Palliative Care after further evaluation and confirmation of eligibility criteria. This dual approach ensures a comprehensive recruitment strategy,

## Appendiks 2

### Studyprotocol, v.1.3 20.12.2024

capturing patients at various stages of the diagnostic phase thus facilitating robust data collection for the study.

#### 5.4.2 Participants' information and written informed consent

The treating physician, nurse or investigator will inform eligible patients about the option to bring relatives to be informed and invited into the study by one of the investigators, which will take place in a private room within the Department of Clinical Oncology and Palliative Care, ZUH, Næstved. All patients eligible for participation will receive a verbal explanation in clear Danish regarding the study's purpose and procedures, the voluntary nature of participation, the guarantee of anonymity, the confidential handling of data, and the implications of their involvement, as detailed in Appendix 4c (*Retningslinjer for afgivelse af mundtlig deltagerinformation*). Patients will be assured that participating in the study will not affect their standard medical treatment and that they can withdraw their consent at any time without any impact on their future care. The following written materials about the PHILUCA study will be distributed: the 1) participant information sheet, 2) the written consent form, 3) the latest version of the brochure "*Before You Make Up Your Mind: The Rights of a Trial Subject in a Clinical Research Project*," and 4) a document outlining our management of personal data according to Region Zealand guidelines (Appendiks 6 *Oplysningspligt*).

Patients will be offered a minimum of 24-hour for consideration, with the opportunity to discuss participation with relatives. After mutual agreement about a contact timepoint, an investigator will contact the patient to determine participation. If participation is agreed and the consent form is signed, the patient will receive a copy, and the baseline test will be scheduled and performed. Patients who decline to participate in the full PHILUCA study will be asked if they would be willing to participate in a minor part of the study by completing the baseline questionnaire and allow that clinical and treatment data is obtained from their medical journal (see Appendix 5, Samtykkeerklæring). This aims to examine the characteristics of these partial decliners and determine if they differ from full participants. Informed consent will be obtained for this purpose before any data about them is collected and stored. The same data from medical records and the baseline questionnaire will be collected from partial participants as from full participants (see part 7.1).

## Appendiks 2

